6.1.3 Other Modality(ies) or Procedures

N/A

6.2 Definition of Dose-Limiting Toxicity

Definition of dose-limiting toxicities, as well as guidelines for DLT management and dose modifications are outlined in Section 7.

Dose escalation will proceed within each cohort according to the following scheme.

Number of Patients with DLT at a Given Dose Level	Escalation Decision Rule
0 out of 3	Enter 3 patients at the next dose level.
≥ 2	Dose escalation will be stopped. This dose level will be declared the maximally administered dose (highest dose administered). Three (3) additional patients will be entered at the next lowest dose level if only 3 patients were treated previously at that dose.
1 out of 3	Enter at least 3 more patients at this dose level. 
 • If 0 of these 3 patients experience DLT, proceed to the next dose level. • If 1 or more of this group suffer DLT, then dose escalation is stopped, and this dose is declared the maximally administered dose. Three (3) additional patients will be entered at the next lowest dose level if only 3 patients were treated previously at that dose.
≤ 1 out of 6 at highest dose level below the maximally administered dose	This is generally the recommended phase 2 dose. At least 6 patients must be entered at the recommended phase 2 dose.

6.3 Dose Expansion Cohorts:

This study will be performed as a phase Ib / II. No expansion cohort will be studied; instead, patients will be added to the phase II study and treated at the RP2D. Monitoring of all safety and toxicity data is done by the Principal Investigator and the Corresponding Organization on a real-time basis as data are entered into Medidata Rave using the Web Reporting Module. All participating sites are expected to notify the Principal Investigator when a DLT has occurred.

6.4 General Concomitant Medication and Supportive Care Guidelines

Patients who are neutropenic should be given appropriate prophylaxis as per the local institutional practice.

Pinometostat is metabolized by CYP3A and is a mild, time-dependent inhibitor of CYP3A. Those patients receiving medications metabolized by CYP3A with narrow therapeutic windows should be monitored carefully while receiving pinometostat. All strong CYP3A4 inhibitors or inducers, including azole antifungals that are strong CYP3A4 inhibitors, are excluded from use in these patients.

Pinometostat is metabolized by CYP450 and patients receiving any medications or substances that are inhibitors or inducers of the CYP450 system should have their medications reviewed and adjusted for interactions as appropriate for local institutional practice.

Medications metabolized by CYP3A with narrow therapeutic windows should be used with caution, as EPZ-5676 is potentially a mild, time-dependent inhibitor of CYP3A. The use or initiation of strong CYP3A4 substrates, inhibitors or inducers will be considered on a case-by-

case basis (based on risk-benefit) only after discussion with the Medical Monitor, and only when no alternative medication is possible.

An updated listing of CYP substrates, inhibitors, and inducers can be found at <http://medicine.iupui.edu/clinpharm/ddis/table.aspx>.

Pinometostat is also metabolized to a minor extent by CYP2C19. It is a substrate of MATE2K and likely a weak substrate for OATP1B3, MATE1, and P-gp. It is also an inhibitor of MATE1 and MATE2K. Use caution when administered with strong inhibitors and inducers of CYP2C19, OATP1B3, P-gp, MATE1, and MATE2K. Use caution with concomitant use of other CYP3A and MATE1 and MATE2-K substrates, especially those with a narrow therapeutic window.

The use of hydroxyurea in patients with acute myeloid leukemia, for control of circulating blast count, is allowed to be given concurrently.

Supportive care measures and symptomatic treatment for any drug-related toxicity may be instituted if clinically indicated. Intermittent use of dexamethasone (10 mg) is permitted as an antiemetic, though chronic steroid use should be discouraged as steroids may be regarded as anti-cancer treatment.

The prophylactic use of hematopoietic colony stimulating factors is prohibited. The therapeutic use of hematopoietic colony stimulating factors should be conducted according to the 2015 ASCO Guideline for use of white blood cell growth factors¹⁹. Blood transfusions may also be administered as needed per the judgment of the Investigator.

Because there is a potential for interaction of pinometostat with other concomitantly administered drugs, the case report form must capture the concurrent use of all other drugs, over-the-counter medications, or alternative therapies. The Principal Investigator should be alerted if the patient is taking any agent known to affect or with the potential for drug interactions. The study team should check a frequently-updated medical reference for a list of drugs to avoid or minimize use of. [Appendix C](#) (Patient Drug Information Handout and Wallet Card) should be provided to patients if available.

6.5 Duration of Therapy

In the absence of treatment delays due to adverse event(s), treatment may continue for 6 cycles. Patients may continue on the study combination if they are deriving clinical benefit. Patients will be taken off the study if one of the following criteria applies:

- Disease progression
- Intercurrent illness that prevents further administration of treatment
- Unacceptable adverse event(s)
- Patient decides to withdraw from the study

- General or specific changes in the patient's condition render the patient unacceptable for further treatment in the judgment of the investigator
- Clinical progression
- Patient non-compliance
- Pregnancy
 - All women of child bearing potential should be instructed to contact the investigator immediately if they suspect they might be pregnant (*e.g.*, missed or late menstrual period) at any time during study participation.
 - The investigator must immediately notify CTEP in the event of a confirmed pregnancy in a patient participating in the study.
- Termination of the study by sponsor
- The drug manufacturer can no longer provide the study agent

The reason(s) for protocol therapy discontinuation, the reason(s) for study removal, and the corresponding dates must be documented in the Case Report Form (CRF).

6.6 Duration of Follow Up

Patients will be followed for 1 month after removal from study or until death, whichever occurs first. Patients removed from study for unacceptable adverse event(s) will be followed until resolution or stabilization of the adverse event.

7. DOSING DELAYS/DOSE MODIFICATIONS

The period of assessment for a dose-limiting toxicity (DLT) will be the first cycle of the phase 1B study.

The starting dose of pinometostat in the phase 1b will be 54 mg/m²/day (actual BSA). The dose will be escalated in two successive cohorts of patients who will be entered sequentially to each dose level (54 mg/m²/day or 90 mg/m²/day). Dose escalation will be performed until \geq Grade 2 (National Cancer Institute (NCI) Common Terminology Criteria for Adverse Events (CTCAE) version 5.0) drug-related (defined as: any AE which cannot be clearly attributed by the Investigator to another cause, such as intercurrent illness or concomitant medication) toxicity in any patient occurs. Dose escalation will stop when the dose reaches 90 mg/m²/day and no further doses will be tested. If the maximum tolerated dose (MTD) is not reached, a recommended phase 2 dose (RP2D) may be used in its place.

Three patients will be assigned to the cohort at which any \geq Grade 2 drug-related toxicity occurred and dose escalation will proceed according to the common 3+3 design. If none of the first 3 patients at the 54 mg/m²/day dose experience first cycle dose limiting toxicity (DLT; see DLT definition below), new patients may be entered at the next higher dose level. If 1 of 3 patients experience a first cycle DLT, up to 3 more patients will be started at that same dose level. If 2 or more experience first cycle DLT, no further patients are started at that dose and a lower dose level of 36 mg/m²/day may be tried.

The MTD is defined as the dose level below which >1 patient out of 3 or ≥ 2 patients out of 6 experience a DLT. The second dose level may begin accrual only if all patients at the first dose level have been observed for a minimum of 28 days, i.e. through the first 28-day cycle. However, if at Day 28 the patient has Grade 3 or 4 neutropenia or thrombocytopenia, (not attributable to persistent leukemia; see DLT definition below), the patient will not begin Cycle 2 and must be observed until Day 42 in order to determine whether a DLT has occurred. In this instance, dose escalation cannot proceed until at least Day 42 so that resolution may be assessed. If patients do not fulfill the definition of severe myelosuppression at Day 28, or if they recover between Days 28 and 42, no hematological DLT will be deemed to have occurred. Patients may then proceed to cycle 2 for further treatment of persistent disease or in the setting of a response.

Once the MTD is reached, the cohort at the MTD will be expanded in the phase II portion of the trial.

A DLT will be defined as a significant suspected adverse reaction or clinically significant abnormal laboratory value assessed as unrelated to disease progression, intercurrent illness, or concomitant medications (only AEs that are incontrovertibly due to an extraneous cause will be excluded as a DLT) and of onset within the first 28 days on study that meets any of the following criteria:

- Any Grade 5 toxicity
- Grade 4 neutropenia lasting ≥ 42 days from start of cycle in absence of evidence of active leukemia

- Any Grade \geq 3 non-hematologic toxicity not clearly resulting from the underlying leukemia EXCEPT:
 - Alopecia
 - Grade 3 fatigue, asthenia, fever, anorexia, or constipation
 - Grade 3 nausea, vomiting, or diarrhea not requiring tube feeding, total parenteral nutrition, or requiring or prolonging hospitalization
 - Infection, bleeding, or other expected direct complication of cytopenias due to active underlying leukemia
 - Grade 3 infusion reaction including cytokine release syndrome, if successfully managed and which resolves within 72 hours
 - Grade 3 or 4 tumor lysis syndrome if it is successfully managed clinically and resolves within 7 days without end-organ damage
 - Grade 3 or 4 isolated electrolyte abnormalities (i.e., those occurring without clinical consequence) that resolve, with or without intervention, to less than Grade 2 in less than 72 hours will not be considered DLT

The above criteria should also be used for AEs for the phase 2 part of the trial. Safety will be assessed by AEs, SAEs, vital signs, physical examinations, and review of biochemistry and hematology laboratory values.

After completion of the first cycle / DLT-assessment period, further toxicities will be managed as for patients treated on the phase 2 portion of the study. Patients who do not achieve a CR or PR after the first cycle of therapy may continue therapy, with the duration of therapy determined as outlined in section 6.5.

During the phase 2, guidance on how to manage common non-hematologic toxicities is given below. If a patient tolerates pinometostat at the MTD and azacitidine at 75 mg/m² but has a hematologic toxicity, the next cycle of azacitidine administration may be delayed out to day 42 while the pinometostat is continued. If the most recent bone marrow on treatment shows persistent leukemia, the patient may continue to be treated with combination therapy with supportive care given for cytopenias.

After discussion with the medical monitor, a lower dose of pinometostat therapy may be considered after the DLT period in the event of toxicities. The dose of azacitidine should remain constant at 75mg/m² daily for 7 days given over a 10-day period at the start of each cycle.

If recurrent hematologic toxicity occurs in someone who has achieved a remission, alternative dosing schedules of pinometostat could be explored as follows:

If the recommended phase II dose is 90 mg/m²/day

Dose Level	Pinometostat Dose
-1	54 mg/m ² /day CIV infusion
0	90 mg/m ² /day CIV infusion

If the recommended phase II dose is 54 mg/m²/day

Dose Level	Pinometostat Dose
-1	36 mg/m ² /day CIV infusion
0	54 mg/m ² /day CIV infusion

Azacitidine administration may be held until up to day 42 of the cycle, but the dosage should not be reduced.

Indications for dose modifications of pinometostat are as follows. For specific concerns not outlined here, please contact the medical monitor.

Nausea	Management/Next Dose for Pinometostat
≤ Grade 1	Continue administration, provide supportive care, monitor
Grade 2	Continue administration, provide supportive care, monitor
Grade 3	Provide supportive care. If tube feeding or TPN are required due to nausea and there is no improvement to ≤ Grade 2 after three days of supportive treatment as per local institutional practice, hold pinometostat until nausea has resolved to ≤ Grade 2. Pinometostat should restarted at one dose level lower.
Grade 4	N/A
*Patients requiring a delay of >2 weeks should go off protocol therapy.	
**Patients requiring > one dose reductions should go off protocol therapy.	
Recommended management: antiemetics.	

Vomiting	Management/Next Dose for Pinometostat
≤ Grade 1	Continue administration, provide supportive care, monitor
Grade 2	Continue administration, provide supportive care, monitor
Grade 3	Provide supportive care. If tube feeding or TPN are required due to vomiting and there is no improvement to ≤ Grade 2 after three days of supportive treatment as per local institutional practice, hold pinometostat until vomiting has resolved to ≤ Grade 2. Pinometostat should restarted at one dose level lower.
Grade 4	Hold therapy until vomiting has resolved to ≤ Grade 2, restart at lower dose if appropriate**
*Patients requiring a delay of >2 weeks should go off protocol therapy.	
**Patients requiring > 1 dose reductions should go off protocol therapy.	
Recommended management: antiemetics.	

Diarrhea	Management/Next Dose for Pinometostat
≤ Grade 1	Continue administration, provide supportive care, monitor
Grade 2	Continue administration, provide supportive care, monitor
Grade 3	If ongoing x 48h, hold therapy until ≤ Grade 2, restart at same dose.

Diarrhea	Management/Next Dose for Pinometostat
	Pinometostat should restarted at one dose level lower*.
Grade 4	Hold therapy until \leq Grade 2, restart at lower dose if appropriate**

Recommended management: Loperamide antidiarrheal therapy Dosage schedule: Adults- 4 mg at first onset, followed by 2 mg with each loose motion until diarrhea-free for 12 hours (maximum dosage: 16 mg/24 hours) Children – 2mg TID dosing may be used for children who are small for their chronological age but are 30kg or greater Adjunct anti-diarrheal therapy is permitted and should be recorded when used. *Patients requiring a delay of >2 weeks should go off protocol therapy. **Patients requiring > one dose reduction should go off protocol therapy.
	

Fever	Management/Next Dose for Pinometostat
\leq Grade 1	Continue administration, monitor
Grade 2	Continue administration, monitor
Grade 3	Hold pinometostat until fever has resolved . Pinometostat should restarted at one dose level lower.
Grade 4	Hold pinometostat until fever has resolved . Pinometostat should restarted at one dose level lower.

Recommended management: antimicrobial or supportive therapy as appropriate based on clinical evaluation
	

Anemia	Management/Next Dose for Pinometostat
\leq Grade 1	Continue administration, monitor
Grade 2	Continue administration, monitor
Grade 3	Continue administration, monitor
Grade 4	If anemia thought to be related to underlying leukemia, continue administration. If anemia thought to be related to drug effect and lasts \geq 14 days, hold pinometostat until anemia has resolved to \leq Grade 1 and restart at dose level -1*

Anemia is anticipated with treatment. *Patients requiring > one dose reduction should go off protocol therapy.
	

Neutropenia	Management/Next Dose for Pinometostat
\leq Grade 1	Continue administration, monitor
Grade 2	Continue administration, monitor
Grade 3	Continue administration, monitor
Grade 4	If neutropenia is thought to be related to underlying leukemia, continue administration. If neutropenia is thought to be related to drug effect and lasts \geq 14 days, hold pinometostat until neutropenia has resolved to \leq Grade 1 and restart at dose level -1*

Neutropenia is anticipated with treatment. Persistent grade 4 neutropenia (lasting \geq 14 days) would necessitate dose de-escalation. Fever with neutropenia necessitating ICU admission should be discussed with the medical monitor. *Patients requiring > one dose reduction should go off protocol therapy.
	

Thrombocytopenia	Management/Next Dose for Pinometostat
≤ Grade 1	Continue administration, monitor
Grade 2	Continue administration, monitor
Grade 3	Continue administration, monitor
Grade 4	If thrombocytopenia is thought to be related to underlying leukemia, continue administration. If thrombocytopenia is thought to be related to drug effect and lasts ≥ 14 days, hold pinometostat until thrombocytopenia has resolved to ≤ Grade 1 and restart at dose level -1*
Thrombocytopenia is anticipated with treatment. *Patients requiring > one dose reduction should go off protocol therapy.	

Bone Marrow Hypocellular	Management/Next Dose for Pinometostat	Management/Next Dose for Azacitidine
≤ Grade 1	Continue administration, monitor	Continue administration, monitor
Grade 2	Continue administration, monitor	Continue administration, monitor
Grade 3	Continue administration, monitor	If hypocellular with no morphologic evidence of leukemia, then hold azacitidine for 2 weeks and repeat a bone marrow biopsy
Grade 4	If persistent aplasia with no morphologic evidence of leukemia after two week azacitidine hold, hold pinometostat for 2 weeks and repeat a bone marrow biopsy	
Inform medical monitor of grade 4 toxicity.		

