9. STATISTICAL CONSIDERATIONS

9.1 Study Design/Endpoints

Phase Ib Safety / Tolerability Run In - Primary Endpoint:

- Safety and tolerability will be assessed by evaluating the number of patients out of 6 who experience a dose-limiting toxicity by cycle 1, day 42, using a standard 3+3 design. Two out of 6 events will lead to a dose-reduction or trial discontinuation as described in the analytic plan.

Phase Ib Safety / Tolerability Run In - Primary Endpoint Analytic Plan:

- An incidence of one in six (or fewer) patients experiencing a DLT, as described in section 7, will be considered a safe and tolerable dose.
- Patients who receive at least a full course of therapy will be considered to be evaluable for toxicity/DLT and will not be replaced unless the PI determines that further additional patients at that dose level are required for safety purposes. Patients who experience a DLT prior to completing a full course of therapy will be accounted for in the safety assessment.
- A standard 3+3 design will be used to study patients on an initial pinometostat dose of 54 mg/m²/day continuous IV infusion, in combination with azacitidine at a dose of 75mg/m² daily for 7 days starting on cycle 1, day 1. If two of six experience a DLT within the first 42 days as defined above, the dose of pinometostat will be decreased to 36 mg/m²/day, and it will be combined with azacitidine at a dose of 75mg/m² daily for 7 days in a separate cohort of patients. If two of six experience a DLT within the first 42 days as defined above, the combination will be deemed intolerable and the study will be terminated. If three patients tolerate the combination of standard-dose azacitidine with pinometostat at 54 mg/m²/day, the pinometostat dose may be escalated to 90 mg/m²/day and tested as per standard 3+3 design. Patients who complete cycle 1 would be allowed to stay on single-agent pinometostat through their day 42 evaluation. Patients who achieve count recovery prior to day 42 may be considered for additional combination therapy with azacitidine and may complete up to 6 cycles of combination therapy as described for patients directly enrolled on the phase II protocol.

Phase II Primary Endpoint:

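### Section 7 holds patients to Day 42 for low platelets to settle DLT status, but its DLT list has no platelet criterion, so one patient can be counted in two ways

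*Combined protocol and SAP*

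**What the plan says.** Section 7 sets the Day 28 hold. It applies "if at Day 28 the patient has Grade 3 or 4 neutropenia or thrombocytopenia, (not attributable to persistent leukemia; see DLT definition below"). Such a patient does not start cycle 2 and "must be observed until Day 42 in order to determine whether a DLT has occurred"; escalation also waits until at least Day 42. The clearing rule follows: "If patients do not fulfill the definition of severe myelosuppression at Day 28, or if they recover between Days 28 and 42", no hematological DLT is recorded.

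The DLT list comes next in the same section. Its lead-in requires onset in the first 28 days and at least one listed criterion. There are three: Grade 5 toxicity; "Grade 4 neutropenia lasting ≥ 42 days from start of cycle in absence of evidence of active leukemia"; and Grade 3 or higher non-hematologic toxicity, with exceptions.

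The DLT count drives the phase Ib decision. Section 6.2 sends 0 of 3 to the next dose level; for 1 of 3 the rule is "Enter at least 3 more patients at this dose level". Section 9.1 calls a dose safe and tolerable on this condition: "An incidence of one in six (or fewer) patients experiencing a DLT, as described in section 7". Two of six leads to dose reduction or discontinuation.

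**The concern.** The hold and the list give different answers for the same patient. The hold treats platelets as something that can turn out to be a DLT; the list gives no criterion that a platelet count can meet. The clearing rule should connect the two, but it depends on *severe myelosuppression*, for which no grade, lineage or count is given, and on recovery, which has no threshold either.

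The patient at issue is leukemia-free, with drug-related Grade 4 thrombocytopenia still present at Day 42. Section 6.3 expects sites to notify the Principal Investigator when a DLT has occurred, so two sites could classify this patient differently. At stake is the phase Ib primary endpoint. The same definition also carries into phase II, through Section 7 and through the stopping rule in Section 9.6.

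**Working it through.** **Hold triggers against the DLT list (Section 7)**

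| Finding at Day 28, not due to leukemia | Triggers the hold | Listed DLT if it persists to Day 42 without leukemia | DLT implied by the recovery sentence |
|---|---|---|---|
| Grade 4 neutropenia | yes | yes | yes |
| Grade 3 neutropenia | yes | no | unclear, term undefined |
| Grade 4 thrombocytopenia | yes | no | yes |
| Grade 3 thrombocytopenia | yes | no | unclear, term undefined |

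Sections 6.2, 9.1, 9.4 and 9.6 add no platelet criterion and no definition of *severe myelosuppression*.

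**Effect of one such patient (no assumed rate)**

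- First cohort with no other DLT: 0 of 3 by the list (enter 3 at the next level); 1 of 3 by implication (add at least 3 at this level).
- Six patients with one other DLT: 1 of 6 by the list (tolerable); 2 of 6 by implication (reduction or discontinuation).

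**What counting platelets would cost (illustration only)**

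The plan's only related figures are the stopping probabilities in Section 9.6. Applying its boundaries exactly (3 in 6, 5 in 12, 6 in 18, 7 in 24, 8 at any point in 30) gives 0.122 at 15% risk and 0.966 at 40%, against the stated 10% and 95%. That difference is a separate matter. The same recursion is used below.

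Assume other DLTs at 10%, and platelet events adding 1 percentage point without overlap, so p goes from 0.10 to 0.11. Neither value comes from the documents.

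- At most 1 DLT in 6, (1−p)^6 + 6p(1−p)^5: 0.531 + 0.354 = 0.886 at p = 0.10; 0.497 + 0.369 = 0.866 at p = 0.11.
- Clearing a level under the 3+3, (1−p)^3 + 3p(1−p)^5: 0.729 + 0.177 = 0.906; 0.705 + 0.184 = 0.889.
- Phase II safety stop under Section 9.6: 0.027; 0.039.

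**The case against.** The strongest reply is that the list alone governs. The hold sentence points to it, its lead-in requires a listed criterion, and Section 9.1 counts DLTs as Section 7 describes them. On that reading platelets are simply not dose-limiting, perhaps on purpose, since Section 7 says thrombocytopenia is anticipated. A watch threshold wider than the DLT threshold is not an error in itself.

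Much of this stands: the list is the more literal reading, and a platelet DLT is implied, not stated. It does not remove the conflict. Section 7 says neutropenia is anticipated too, yet neutropenia is listed. Section 9.1 refers to Section 7 as a whole, which holds both the list and the recovery sentence. And if platelets were never meant to count, a platelet hold whose stated purpose is to determine DLT status cannot serve that purpose. Serious bleeding may be a DLT, but it is a different event from a Day 42 count. The sign-off and CTEP review in Section 13.1 add oversight without saying whether the event counts.

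Three stronger readings are tempting, and the documents do not support them.

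- *The platelet hold decides nothing.* It still delays cycle 2 and escalation, and on the implied reading it does settle DLT status.
- *The dose-modification table proves that the dose was not tolerated.* It says "If thrombocytopenia is thought to be related to drug effect and lasts ≥ 14 days, hold pinometostat until thrombocytopenia has resolved", with restart at level -1. The same 14-day Grade 4 rule covers anemia, which has no DLT criterion, and neutropenia, whose DLT needs 42 days. It shows only that dose modification and DLT use different thresholds.
- *The 20% and 40% response rates in Section 9.1 give the leukemia-free share, and so an upper bound on frequency.* They are design hypotheses for response at any time over six cycles, not status at Day 42. Under Section 12.1.4.1, CR and PR also require platelets above 100,000 per microliter, which excludes Grade 4 thrombocytopenia.

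**Conclusion.** The concern holds as an internal contradiction in the rule that feeds the phase Ib primary endpoint. Unrecovered drug-related Grade 4 thrombocytopenia without leukemia is not a DLT by the list and is one by implication, and no definition resolves it. That one patient can change an escalation or tolerability decision follows from Sections 6.2 and 9.1 alone. How often it would happen cannot be said, and no upper range should be claimed; the 10% and 11% risks above show direction and rough cost only. No figure in the plan is wrong on this account. The text needs correcting whichever way the sponsor intends it.

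**What to change.** **If platelets are meant to be dose-limiting**

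- Add a DLT criterion: Grade 4 thrombocytopenia (untransfused platelet count) lasting at least 42 days from start of cycle, without evidence of active leukemia, in patients without Grade 4 thrombocytopenia at baseline. The qualifiers are needed because Section 6.4 allows transfusion and Section 3.1.6 sets no platelet minimum.
- Define *severe myelosuppression* as Grade 4 neutropenia or thrombocytopenia without active leukemia, and use that term for the DLT hold. Recovery then means no longer meeting it.
- State any Grade 3 hold separately, as a dosing delay only.

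**If platelets are deliberately not dose-limiting**

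- Remove thrombocytopenia from the DLT hold, and report by dose level the number of leukemia-free patients with Grade 4 thrombocytopenia at Day 42.

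**In either case**, list a Day 42 blood count for held patients. Section 9.1 relies on that visit (patients "would be allowed to stay on single-agent pinometostat through their day 42 evaluation"), but the Section 11 calendar shows no blood count in weeks 6 to 8.

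The cost is a few lines of wording and one calendar entry. The added criterion makes a dose level fail somewhat more often. Because Section 9.6 mirrors the DLT definition, it also raises the counted risk in phase II and so the chance of a safety stop. The operating characteristics should be recalculated at whatever event rate the sponsor considers plausible.

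### For prolonged drug-related grade 4 cytopenia, Section 7 both continues and holds pinometostat with no stated precedence, Section 9.1 adds no exception, and the restart dose is unclear for some patients

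*Combined protocol and SAP*

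**What the plan says.** **Section 7, text on phase II management.** An introductory sentence describes the guidance that follows as being for common non-hematologic toxicities. For a hematologic toxicity in a patient who otherwise tolerates the regimen, "the next cycle of azacitidine administration may be delayed out to day 42 while the pinometostat is continued". Persistent leukemia has its own sentence. A lower pinometostat dose is optional: it may be considered with the medical monitor after the DLT period, and "If recurrent hematologic toxicity occurs in someone who has achieved a remission, alternative dosing schedules of pinometostat could be explored as follows". Two small tables then define level -1 as 54 mg/m²/day if the RP2D is 90, and 36 if it is 54.

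**Section 7, toxicity tables.** For drug-related grade 4 neutropenia lasting at least 14 days, the instruction is to "hold pinometostat until neutropenia has resolved to" grade 1 or lower and restart at level -1. The note adds that such persistence "would necessitate dose de-escalation". The anemia and thrombocytopenia tables carry the same hold and restart. The marrow table, at grade 3, continues pinometostat and says of azacitidine: "If hypocellular with no morphologic evidence of leukemia, then hold azacitidine for 2 weeks and repeat a bone marrow biopsy". At grade 4, if aplasia persists "after two week azacitidine hold, hold pinometostat for 2 weeks".

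**Phase Ib timing.** Section 7 says: "The period of assessment for a dose-limiting toxicity (DLT) will be the first cycle of the phase 1B study". Later toxicities are then managed as in phase II. A patient with unresolved, non-leukemic grade 3 or 4 neutropenia or thrombocytopenia at day 28 does not start cycle 2 and is watched to day 42. The hematologic DLT is grade 4 neutropenia lasting at least 42 days from cycle start. Section 9.1 reads the DLT at day 42 and permits patients who complete cycle 1 to remain on single-agent pinometostat until then.

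**Section 6.1.** Level -1 is 36, Level 1 is 54 and Level 2 is 90 mg/m²/day.

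**The concern.** A site that follows the Section 7 paragraph, or the Section 9.1 permission, can keep infusing a patient whom the cytopenia tables say to hold. The paragraph makes reduction optional and ties it to recurrence in remission; the tables make it mandatory at first occurrence. The neutropenia table itself says "Neutropenia is anticipated with treatment", so the situation is foreseeable.

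At stake is consistent dosing of patients with prolonged severe cytopenia. In phase Ib, it is also whether a patient is on or off pinometostat while the 42-day neutropenia DLT is being decided. Section 7 does not say whether the infusion runs during that observation period. Section 9.6 carries the DLT definition into the phase II safety stop, so the same uncertainty about drug status follows it there.

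**Working it through.** There is no stated figure to reproduce. The check sets the instructions side by side and adds short arithmetic.

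**Step 1. One patient, several instructions.** Take drug-related grade 4 neutropenia of 14 days, with no leukemia in the marrow.

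| Source | Pinometostat | Reduction |
|---|---|---|
| Section 7 text | continues; azacitidine may be delayed | optional |
| Section 7 neutropenia table | held to grade 1 or lower | required, to level -1 |
| Section 7 marrow table, if also hypocellular at grade 3 | continues; azacitidine held 2 weeks | none stated |
| Section 9.1 (phase Ib, to day 42) | may continue | not mentioned |

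The text sets no limit of grade, duration or attribution on the hematologic toxicity it covers. Persistent leukemia is dealt with separately, so the text reaches leukemia-free cytopenia as well. No sentence ranks these sources.

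**Step 2. Days 29 to 42 in phase Ib.** If the DLT period is the 28-day first cycle, phase II management starts on day 29. The earliest hold day is then max(29, onset + 14), and the time left is 42 minus that day. Onset days are illustrative.

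| Onset of grade 4 | 14-day trigger | Earliest hold | Days left to day 42 |
|---|---|---|---|
| 1 | 15 | 29 | 13 |
| 10 | 24 | 29 | 13 |
| 14 | 28 | 29 | 13 |
| 20 | 34 | 34 | 8 |

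If the assessment period is instead taken to run to day 42, as in Section 9.1, the tables do not yet apply and the permission stands. So for 8 to 13 days in these examples, drug status depends on which section is followed.

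**Step 3. The restart dose.**

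- Phase Ib patient on 90: Section 7 gives 54 (if the RP2D becomes 90), a cut of 1 − 54/90 = 40%. Section 6.1 gives 36, a cut of 1 − 36/90 = 60%. Section 7's value is keyed to an RP2D that does not yet exist.
- Patient on 54: Section 6.1 and Section 7's table for an RP2D of 54 both give 36, a cut of 1 − 36/54 = 33%.
- Assigned dose 36: no lower level is given.
- Phase II with an RP2D of 54 or 90: Section 7 fixes a single value.

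**Step 4. Can an effect on the DLT count be computed?** It needs three inputs that the documents do not give: the share h with such neutropenia, the other DLT risk, and the chance r that the neutropenia reaches day 42 with and without a hold. For illustration only, assume h = 0.20 and other risk 0.10. Then p = 1 − 0.90 × (1 − 0.20r), and a 3+3 level fails with probability P(≥2 of 3) + P(1 of 3) × P(≥1 of next 3).

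| Assumed r | p | 3+3 failure |
|---|---|---|
| 0.50 (continue) | 0.190 | 0.27 |
| 0.50 (hold, no effect on recovery) | 0.190 | 0.27 |
| 0.40 (hold) | 0.172 | 0.23 |
| 0.20 (hold) | 0.136 | 0.16 |

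The difference runs from zero to 0.11, determined entirely by the assumed r.

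**The case against.** The strongest reply is that specific rules override general ones. The paragraph is permissive and mainly concerns azacitidine timing. The sentence directly before the toxicity tables presents them as the indications for modifying pinometostat, and the cytopenia rows are narrow: grade 4, drug-related, at least 14 days. This stands as the natural reading. It does not close the point, because the earlier lead-in confines the guidance below it to non-hematologic toxicities and no precedence is written down.

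A reader might infer from the marrow table that two equally specific rows contradict each other. That goes too far. The marrow row responds to biopsy cellularity and the neutropenia row to blood counts; a site can satisfy both by taking the stricter pinometostat action. One sentence saying so is enough.

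A reader might also take Section 9.1 as ordering pinometostat through day 42. It is a permission. What remains is the missing exception, together with the 28-day versus 42-day description of the assessment period.

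On the restart dose, Section 6.1 names an escalation cohort, while Section 7 supplies the reduction table, so phase II is clear once the RP2D is 54 or 90. A patient already reduced once goes off therapy if a further reduction is needed. The medical-monitor clause can cover a lower dose in phase Ib, but it does not decide between hold and continue.

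Oversight is close: the Principal Investigator reviews safety data in real time and signs off dose decisions, and there are roughly weekly safety conferences. This limits divergence between sites without telling anyone which instruction is correct.

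**Conclusion.** The inconsistency is real and its scope is limited. Section 7's text and tables differ on holding and reducing pinometostat for drug-related grade 4 cytopenia of 14 days or more. Section 9.1 makes no exception for it, and drug status on days 29 to 42 is not specified for a phase Ib patient under observation. The restart dose is unclear only for phase Ib patients before an RP2D exists (in numbers, those on 90: a 40% or 60% cut) and for anyone assigned 36.

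A reader might infer that sites would report different DLT counts, and that the 3+3 decision or the phase II stop would shift. The documents do not support that step. They give neither the frequency of such neutropenia nor the effect of a hold on recovery, and if a hold does not speed recovery the shift is zero. Nor are all 36 phase II patients affected: the rule concerns only those with prolonged drug-related grade 4 cytopenia, and the neutropenia DLT also requires no evidence of active leukemia.

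The supported conclusion is inconsistent dosing instructions with a safety bearing. Severity: minor to moderate.

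**What to change.** 1. In Section 7, state: *For drug-related grade 4 cytopenia lasting 14 days or more without leukemia in the marrow, the tables govern; the paragraph on continuing pinometostat applies to lesser hematologic toxicity. If the neutropenia and marrow rows both apply, the stricter pinometostat action is taken.* Correct the lead-in so that it no longer describes the tables as covering non-hematologic toxicities only.
2. In Section 9.1, add to the day-42 permission: *unless the Section 7 tables require a hold*. Apply this to all phase Ib patients, and show on-drug or off-drug status in the DLT listing.
3. In the toxicity tables, replace level -1 with *next lower level than the assigned dose*: 90 to 54, and 54 to 36. At 36: hold, then either resume at a dose agreed with the medical monitor or go off protocol therapy.

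The cost is wording in Sections 7 and 9.1, one table row and one listing column, with no added patients, visits or procedures. The study team must confirm the hold rule, which is a clinical decision and may mean less pinometostat exposure for some patients. Section 13.1 already requires an amendment before phase II opens, but the phase Ib parts are needed sooner than that.
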